## **5 SUBJECT SELECTION**

Patients who are scheduled to undergo CRS-HIPEC in the operating room who can provide informed consent, have a good performance status (ECOG  $\leq 2$ ), and have no known allergy or prior reaction to fluorescein, ICG or iodine, are eligible.

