## **6 STUDY PROCEDURES**

### **6.1 BASELINE EVALUATIONS**

Standard presurgical assessment with labs and studies as determined by the preoperative Anesthesia clinic based upon their established guidelines.

The following will be performed within 1 week prior to the planned microscopic observation:

- Informed consent: Must be completed prior to receiving any study-related procedures.
- Medical history
- Physical examination, including vital signs (i.e., temperature, heart rate, respiratory rate, blood pressure, body weight, and height).
- If determined to be eligible for the study and after giving informed consent, a skin-prick test to determine sensitivity and risk of anaphylaxis to fluorescein and a patch test for ICG will be

performed by the Principal Investigator. For testing allergic response to fluorescein, a sterile Duotip® lancet (Lincoln Medical, USA) is used in 3 separate areas of skin on the forearm. The skin-pricks will include 4 microliters of 10% fluorescein, histamine chloride (10 mg/ml) [positive control], and 50% saline solution [negative control] administered in areas of skin prepped with an alcohol pad. After 30 minutes, the appearance of a wheal greater than 3 mm in diameter is considered a positive test result in the context of the appropriate positive and negative control. If a positive test is noted, the patient will no longer be eligible for this study. For comfort and relief of any skin irritation/pruritis, the patient will be offered an anti-histamine (fexofenadine [Allegra®] 30 mg po x 1) following the skin-prick test if necessary. The patient will also be screened for a history of allergic reaction to iodine or iodinated contrast dyes.

- If indicated by anesthesia pre-op assessment (standard operating procedure for pre-op clinic)  
- Hematology [i.e., CBC (with or without differential, auto or manual), ANC, and platelets].
- A complete metabolic panel (CMP): chloride, Co2, potassium, sodium, BUN, glucose, calcium, creatinine, total protein, albumin, total bilirubin, alkaline phosphatase, AST, ALT, A/G ratio, BUN/creatinine ratio, osmol (Calc), anion gap).

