#### Study Calendar

	Pre-operative Visit	Surgery	Post-operative Visit
History and Physical	X		
Informed consent	X		
Fluorescein skin prick test	X		
Tests as medically indicated	X		
CRS-HIPEC with intra-op IVM		X	
Post-surgical monitoring in recovery and inpatient stay		X	
Review of pathology			X
Routine cancer surveillance			X

- At the completion of the surgery, if gross tumor is entirely debulked or ablated, then patients are considered disease free. Treatment response will be based upon the presence of a recurrence of tumor at either the primary site, locoregional recurrence (peritoneum) or metastatic sites.
- The time to recurrence will determine the standard length of clinical follow up. However, for this study, a 10-year limit will be placed on clinical data collection during the standard clinical follow up. After a patient is enrolled, the duration of data collection will end at 10 years from the time of microscopic observation (surgery). These data (time of recurrence

and/or survival) will be correlated with findings from the one-time, initial IVM observation for the defined 10-year period of data collection.

- The surveillance data (no evidence of disease, disease recurrence, death) will be stored in a secured database and matched to the microscopic observation data. These data will serve as the basis for statistical comparisons of microscopic findings and clinical outcomes to be performed by our study statistician as described in section 9.

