A matched analysis will be performed for observations of microvasculature between the peritoneal tumor implants and normal tissue. For dichotomous variable comparisons between vessel structure (normal vs aberrant), vessel branching patterns (normal vs aberrant), or detection of intravital dye (present vs absent), a McNemar's test will be performed. For continuous variable comparisons between blood vessel density and average blood flow rate, a paired t test will be performed.

Associations between characteristics for the baseline (normal peritoneal microvasculature observed surrounding the tumor implant site) and tumor implant itself will be depicted with graphics, correlations, and model results.

Adverse event and complication rates will be described using upper one-sided 95% Clopper Pearson confidence limits.

Overall survival will be defined as the duration of time from diagnosis to time of death. Disease specific survival will be defined as the time from CRS-HIPEC to death due to recurrence. Overall survival and disease specific survival will be generated using standard Kaplan-Meier methodology.

A maximum of 30 subjects will be enrolled in this study (initially 10 to determine feasibility and then 20 additional subjects if deemed feasible). The accrual rate is estimated at one subject per month, and the estimated study duration is 30 months.

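### Overall survival is timed from diagnosis by standard Kaplan-Meier although patients enter just before surgery, so it overstates survival from diagnosis and does not share a time axis with disease-specific survival

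*Combined protocol and SAP*

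**What the plan says.** Section 9 (Statistical Methodology) gives the two survival outcomes different starting points:

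- Overall survival (OS): "Overall survival will be defined as the duration of time from diagnosis to time of death".
- Disease-specific survival (DSS): "Disease specific survival will be defined as the time from CRS-HIPEC to death due to recurrence".
- Estimator: "Overall survival and disease specific survival will be generated using standard Kaplan-Meier methodology".

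Other sections fix when a patient comes under observation:

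- Section 5 describes the eligible group as "Patients who are scheduled to undergo CRS-HIPEC in the operating room who can provide informed consent".
- Section 6.1 introduces consent and baseline assessment with "The following will be performed within 1 week prior to the planned microscopic observation". Section 1.2 instead puts the preoperative visit at least one week before surgery. The two statements differ, but both place entry close to the operation.
- The notes under the Study Calendar count the 10-year data collection from surgery. They say that recurrence and survival data "will be correlated with findings from the one-time, initial IVM observation for the defined 10-year period of data collection".

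Survival enters the plan through secondary objective 3 (Section 3.2) and secondary endpoint 3 (Section 3.3), which correlate the microvascular findings with tumor-specific and overall survival. The documents contain no delayed-entry method, no reason for using two origins, and no definition of diagnosis (primary tumour or carcinomatosis).

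**The concern.** A patient who dies after diagnosis but before being scheduled for CRS-HIPEC can never be enrolled. Every enrolled patient has therefore survived the whole diagnosis-to-entry interval by design. Standard Kaplan-Meier from diagnosis treats all enrolled patients as at risk from time zero, so it credits them with time in which no death could have been recorded. This is left truncation, and it raises the curve.

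Three things are at stake:

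- A published OS from diagnosis would look better than survival from diagnosis really is.
- OS and DSS could not be read on one time axis, because each patient's OS time is longer by an unreported interval.
- The microscopy finding is made at surgery. If the interval differs between patients with and without a given finding, it could create or hide an association with OS.

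A smaller point concerns the DSS event, which is death due to recurrence. The Study Calendar notes say that "if gross tumor is entirely debulked or ablated, then patients are considered disease free". Read literally, a death from residual tumour after incomplete debulking is not a DSS event. That does not match the tumor-specific survival named in Sections 3.2 and 3.3.

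**Working it through.** The plan gives no survival rate, median or event count, so there is no figure to reproduce. The direction of the bias follows from the design. Its size needs assumptions.

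**Assumed inputs.** Survival T from diagnosis has constant hazard and median 24 months, so λ = ln 2 / 24 = 0.02888 per month. The diagnosis-to-surgery interval I is uniform on (a, b) among diagnosed patients and independent of T. A patient enters only if T > I. Three ranges are used: 0–2, 2–12 and 3–24 months.

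**Standard Kaplan-Meier from diagnosis** estimates P(T > t | T > I). For t ≥ b this is exp(−λt) / E, where E = P(T > I) = [exp(−λa) − exp(−λb)] / [λ(b − a)]. The median is then 24 − ln(E) / λ.

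- 0–2: E = (1 − 0.9439) / 0.0578 = 0.972; median 24 + 1.0 = 25.0.
- 2–12: E = (0.9439 − 0.7071) / 0.2888 = 0.820; median 24 + 6.9 = 30.9.
- 3–24: E = (0.9170 − 0.5) / 0.6065 = 0.688; median 24 + 13.0 = 37.0.

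**Delayed-entry Kaplan-Meier** adds each patient to the risk set at surgery. It estimates survival from diagnosis conditional on reaching the shortest interval a. With constant hazard its median is a + 24.

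| Interval (months) | Standard median | Delayed-entry median | Difference | Standard S(12) | Delayed-entry S(12) |
|---|---|---|---|---|---|
| 0–2 | 25.0 | 24.0 | 1.0 | 73% | 71% |
| 2–12 | 30.9 | 26.0 | 4.9 | 86% | 75% |
| 3–24 | 37.0 | 27.0 | 10.0 | 94% | 77% |

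Simulation with 400,000 draws agrees to within 0.1 month. Timed from surgery, the median is about 24 months in all three cases, which is a property of the constant hazard.

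**Sensitivity.** Over true medians of 12, 24 and 48 months and Weibull shapes 0.8, 1.0 and 1.5, the median is overstated by 0.1–2.6 months (0–2), 1.6–8.1 months (2–12) and 4.4 to about 15 months (3–24). With exponential intervals (means 3–24 months) and true medians of 24, 36 and 60 months, the overstatement is about 3 to 20 months.

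**Association with microscopy findings.** The plan names no survival test. Suppose a 5% log-rank test is used with 30 patients, no true effect, and censoring 120 months after surgery. Simulated rejection rates with OS timed from diagnosis are:

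| Link between finding and interval | 0–2 | 2–12 | 3–24 |
|---|---|---|---|
| None | 6% | 6% | 6% |
| 75/25 | 6% | 7% | 8% |
| Perfect | 6% | 8% | 14% |

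Timed from surgery, the rate is about 6% throughout.

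**The case against.** The strongest reply is that the bias is relative to a target the plan never states. Objective 3 concerns correlation among enrolled CRS-HIPEC patients. There is no historical benchmark, survival threshold or planned OS-versus-DSS comparison. Read as conditional on reaching CRS-HIPEC, a curve from diagnosis is interpretable. That is fair, but Section 9 does not label it so, and a reader will take the stated definition at face value.

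Several further points stand as limits on importance:

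- The interval is unknown. If it is short, the bias is about a month.
- On the figures above, the correlation is barely affected without a strong link between finding and interval. The documents neither state nor exclude such a link.
- With 30 patients and full follow-up, sampling error is large. In the 2–12 month case the standard median has a 95% sampling range of about 21 to 45 months. Noise limits the practical consequence but does not remove a systematic shift.
- Section 1.1 names carcinomatosis as the study disease, which suggests that diagnosis means diagnosis of carcinomatosis. Section 9 does not say so.

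One objection bears on the remedy. Delayed-entry Kaplan-Meier requires the interval to be independent of survival, and patients are selected for surgery. In the 3–24 month case, a correlation between interval and survival of +0.5 to −0.5 moved the delayed-entry median from about 13 to 35 months, against a correct 27. Timing OS from surgery does not need that assumption.

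**Conclusion.** The concern holds. As written, the OS curve includes time in which no enrolled patient could have died, so it overstates survival from diagnosis whenever deaths can occur between diagnosis and entry. It also has a different origin from DSS and from the 10-year data collection.

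The direction is certain; the size is not. It ranges from about 1 to 10 months in the median for the three assumed intervals at a true median of 24 months, and more widely under other assumptions. The effect on objective 3 is small unless the interval is strongly related to the microscopy finding.

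This should be corrected, but it concerns a secondary outcome in at most 30 patients. The primary feasibility endpoint and the Part 1 go/stop rule are untouched.

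**What to change.** In Section 9, define OS as time from CRS-HIPEC (the microscopy observation) to death from any cause. This matches the origin of DSS and of the 10-year data collection.

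If OS from diagnosis is also wanted, define diagnosis, let patients enter the risk set at surgery, and label the curve descriptive. State that it is conditional on surviving to the shortest observed interval and that it assumes the interval is independent of survival.

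As a minor wording change, define the DSS event as death due to the peritoneal malignancy, whether recurrent, persistent or progressive.

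The cost is two sentences in Section 9. The surgery date is already needed for DSS, so no new data are collected. Reported OS will be shorter than under the present definition.

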#### 3.2 SECONDARY OBJECTIVES - PART II (20 PATIENTS):

1. Compare the microscopic observation of the tumor-associated vessels with normal tissue (peritoneal surface) in each individual subject.
2. Correlate the microscopic observations of the tumor-associated vessels with pathologic grade of tumor implants.
3. To correlate the microscopic observation of the microvasculature with tumor-specific and overall survival.

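### Disease-specific survival counts only deaths due to recurrence, so read literally it omits cancer deaths in patients left with residual tumor

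*Combined protocol and SAP*

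**What the plan says.** Section 3.2 sets the objective: "To correlate the microscopic observation of the microvasculature with tumor-specific and overall survival". The synopsis, Section 3.3 and Section 9 repeat it.

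Section 9 makes it operational: "Disease specific survival will be defined as the time from CRS-HIPEC to death due to recurrence". The estimator follows: "Overall survival and disease specific survival will be generated using standard Kaplan-Meier methodology". Section 9 gives no censoring rule and does not say how deaths from other, postoperative or unknown causes are handled.

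The Study Calendar notes in Section 6.3 say that "if gross tumor is entirely debulked or ablated, then patients are considered disease free". They give no status for a patient whose tumor is not fully removed. Later disease is described only as recurrence: "Treatment response will be based upon the presence of a recurrence of tumor at either the primary site, locoregional recurrence (peritoneum) or metastatic sites". The surveillance data to be stored are three states (free of disease, recurred, dead), without cause of death or a state for persisting or progressing tumor. On duration, "a 10-year limit will be placed on clinical data collection".

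Section 7.2.1 does recognise death from tumor progression, but only to exclude it from serious adverse event reporting.

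**The concern.** The endpoint does not match its objective. Tumor-specific survival should count every death caused by the malignancy. The definition counts those that follow a recurrence, and a recurrence in the ordinary sense requires that the disease was first cleared. By making disease-free status conditional on complete removal, the Study Calendar notes allow for patients in whom it was not.

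If a residual-disease patient dies of cancer and the definition is followed to the letter, there is no event. Standard Kaplan-Meier then has only one place to put the patient: censored at death. Kaplan-Meier treats a censored patient as having the same future risk as those still followed. Here the censored patients would be those with the worst prognosis, so the censoring is informative and the curve is pushed upward.

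The association with microvasculature is exposed too. If abnormal vessels go with residual tumor, the omitted events fall mostly in the abnormal group, and the estimated link is distorted. Sections 1.3 and 1.5 name prognostic information as a potential benefit, so this association matters to the study's purpose.

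**Working it through.** The plan states no survival rate, event count or power for this endpoint, so there is no figure to reproduce. The check compares the curve as literally defined with the curve that counts all cancer deaths.

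**Inputs (all assumed; the documents give none)**
- h1 = 0.15 per year: hazard of cancer death after complete debulking, every such death counted as due to recurrence.
- h2 = 0.70 per year: hazard of cancer death with residual tumor, none counted (the strictest literal reading).
- f: share with residual tumor, 0% to 30%.
- T = 3 years. Other-cause mortality is taken as equal and independent in the two groups; it then cancels from both curves.

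**Formulas**
- All cancer deaths counted: S = (1−f)·exp(−h1·T) + f·exp(−h2·T).
- As written: the Kaplan-Meier hazard at time t is h1 times the debulked share of those still at risk. With r = f/(1−f) and d = h2−h1, integrating gives L = [(1+r)/(exp(d·T)+r)]^(h1/d).

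**Worked case, f = 10%**
- S = 0.9×exp(−0.45) + 0.1×exp(−2.1) = 0.9×0.6376 + 0.1×0.1225 = 0.586.
- r = 0.1111, d = 0.55, exp(1.65) = 5.207, h1/d = 0.2727. L = (1.1111/5.3181)^0.2727 = 0.652.
- Gap: 6.6 points.

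| Residual share | As written | All cancer deaths | Gap (points) |
|---|---|---|---|
| 0% | 63.8% | 63.8% | 0 |
| 2% | 64.1% | 62.7% | 1.3 |
| 5% | 64.5% | 61.2% | 3.3 |
| 10% | 65.2% | 58.6% | 6.6 |
| 20% | 66.9% | 53.5% | 13.4 |
| 30% | 68.8% | 48.3% | 20.5 |

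The as-written curve rises as the cohort gets sicker, because the sickest patients leave the risk set without an event.

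**Sensitivity to the residual-disease hazard.** With h2 = 0.30, d = 0.15 and h1/d = 1. At f = 10%, L = 1.1111/(1.5683+0.1111) = 0.662 and S = 0.9×0.6376 + 0.1×0.4066 = 0.615, a gap of 4.7 points. At f = 30%, L = 0.715, S = 0.568 and the gap is 14.7 points.

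**A second set of assumptions, at 5 years.** Take net survival of 50% if debulked and 10% if residual, so h1 = −ln(0.5)/5 = 0.139 and h2 = −ln(0.1)/5 = 0.461. As written: 51.8%, 53.9% and 56.3% at 10%, 20% and 30% residual. All cancer deaths: 46.0%, 42.0% and 38.0%. The gap is about 6 to 18 points.

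**Effect on the association.** Suppose 40% of patients with abnormal vasculature and 10% of those with normal vasculature have residual tumor, with h1 = 0.15 and h2 = 0.70. Three-year survival counting all cancer deaths is 43.2% against 58.6%. As written it is 70.9% against 65.2%, so the order is reversed. This shows that a reversal is possible, not that it is expected.

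**Other-cause deaths, a separate matter.** With cancer hazard a = 0.15 and other-cause hazard b = 0.02 to 0.06 per year, 1 minus Kaplan-Meier is 1−exp(−a·T), and the cumulative incidence is a/(a+b)·[1−exp(−(a+b)·T)]. At 5 years: 52.8% against 50.5% to 46.4%, a difference of 2 to 6 points. At 10 years: 77.7% against 72.1% to 62.7%, a difference of 6 to 15 points. This matters only if the curve is read as the actual probability of dying of cancer.

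**The case against.** The strongest reply is that the authors may use recurrence loosely for any cancer death. The plan nowhere says that residual-disease deaths are censored; that follows only from the literal definition combined with standard Kaplan-Meier. This stands as a limit on the claim. But the same narrow term governs both the Study Calendar notes and Section 9, while Section 7.2.1 names progression deaths separately. Two analysts could fairly classify the same death differently.

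A reader might go further and infer that patients with residual tumor cannot contribute any event. The documents do not support that. The sentence on recurrence sites is not restricted to disease-free patients, so a new metastatic lesion in a patient with residual peritoneal tumor could be counted. The gaps computed here are therefore upper values for the chosen hazards and shares.

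Overall survival has no restriction by cause, so these deaths do enter the companion endpoint. That is correct and lowers the stakes, although overall survival runs from diagnosis and is not a direct substitute.

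The share with residual disease may be small. Synopsis exclusion 8 removes patients whose high disease burden favours other treatment, and the gap is only about 1 to 3 points at 2% to 5% residual. Sampling error is also large: with 30 patients and survival of 0.586, ignoring censoring, the standard error is √(0.586×0.414/30) = 0.090, or 9 points, more than the gap at 10% residual. Both points stand on practical impact. The bias itself does not diminish with more patients.

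Finally, a reader might infer that Kaplan-Meier is the wrong estimator because it censors other-cause deaths. The documents do not support that either. Such censoring is the usual convention for disease-specific survival and is the data handling behind cause-specific hazards, which suit the stated correlation objective. The plan never says it will read 1 minus Kaplan-Meier as an absolute risk.

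**Conclusion.** The point holds for the event definition. As worded, disease-specific survival is narrower than the tumor-specific survival of the objective, and cancer deaths with residual tumor would be censored informatively. Under the main assumed hazards the 3-year curve is too high by 0 points with no residual disease, about 3 at 5%, 7 at 10% and 20 at 30%. Every hazard and share is an assumption, and if all patients are fully debulked the problem disappears. Distortion of the microvasculature association requires that vasculature be related to residual disease, which is unknown.

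Using Kaplan-Meier with other-cause deaths censored is not an error here. It needs a companion estimate only if an absolute probability of cancer death is reported.

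The endpoint is secondary, has no hypothesis or power statement, and rests on at most 30 patients. Priority is low.

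**What to change.** In Section 9, define the event as death due to the peritoneal malignancy, whether recurrent, residual or progressive. State how postoperative, other-cause and unknown-cause deaths are handled, and the censoring date for patients alive.

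Add cause of death and completeness of cytoreduction to the surveillance data listed in the Study Calendar notes. Cause of death is already needed to apply the existing definition but is not listed there.

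Keep cause-specific Kaplan-Meier, with other-cause deaths censored, for the association with microvasculature. If an absolute probability of cancer death is reported, show beside it the cumulative incidence (Aalen-Johansen), with other-cause and postoperative deaths as competing events. Overall survival can stay on Kaplan-Meier.

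The cost is a few sentences in Section 9, one or two data items and a small amount of extra analysis. Sample size and study procedures do not change.

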## 9.1 RANDOMIZATION

This is a nonrandomized study. No randomization scheme will be generated. Subjects will be assigned to a treatment group based on their date of qualification for participation.

